### **8.2.7. Investigational Product Exposure**

This analysis will be based on the Safety Set.

Total drug exposure (in mg), total exposure duration to IP (in days), and percent of planned exposure received (in %) will be summarized for the Safety Set by actual treatment group.

Total drug exposure (in mg) is defined as the total IP in mg for SAGE-718 that was taken during the study. Total drug exposure for participants randomized to placebo is zero unless the participant has taken SAGE-718 by mistake, in which case the total exposure comes from SAGE-718 exposure and is summarized under SAGE-718 as eth actual treatment. If a participant skips a dose on any of the days, the dose taken is 0 mg.

Total exposure duration to IP (in days) is defined as the date of the last dose minus the date of first dose plus 1. Note that this does not exclude days when the dose has been missed.

Percent of the planned exposure received is defined as the total drug exposure, divided by planned exposure, times 100.

- 1) For participants randomized to SAGE-718 who complete the treatment period, planned exposure is (Date of Day 28 visit – First Dose Date of 1.2 mg) times 1.2 mg plus
  - a. (Date of Day 84 visit – Date of Day 28 visit+1) times 0.9 mg if Study Day of Day 84 visit is >81 and <87.
  - b. (First Dose Date of 1.2 mg + 86 – Date of Day 28 visit) times 0.9 mg if Study Day of Day 84 Visit > 86.
  - c. (First Dose Date of 1.2 mg +82 – Date of Day 28 visit) times 0.9 mg if Study Day of Day 84 Visit <82.
- 2) For participants who discontinue the treatment earlier than Day 28, the planned exposure is (Last Dose Date – First Dose Date + 1) times 1.2 mg for participants randomized to SAGE-718.

- 3) For participants who discontinue the treatment on or after Day 28 but prior to Day 84, the planned exposure is (Date of Day 28 visit – First Dose Date of 1.2 mg) times 1.2 mg plus (Last Dose Date of 0.9 mg – First Dose Date of 0.9 mg +1) times 0.9 mg
- 4) For participants who cannot tolerate 1.2 mg prior to Day 28 therefore received 0.9 mg for the remainder of the treatment period, the planned exposure is (Last Dose Date of 1.2 mg – First Dose Date of 1.2 mg + 1), times 1.2 mg plus
  - a. (Date of Day 84 visit – First Dose Date of 0.9 mg +1) times 0.9 mg if Study Day of Day 84 visit is >81 and <87.
  - b. (First Dose Date of 1.2 mg + 86 – First Dose Date of 0.9 mg) times 0.9 mg if Study Day of Day 84 Visit > 86.
  - c. (First Dose Date of 1.2 mg +82 – First Dose Date of 0.9 mg) times 0.9 mg if Study Day of Day 84 Visit <82.
- 5) For participants who never received SAGE-718, this measure is not applicable.

By-participant listing of extent of exposure will also be provided.

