### **8.2.8. Investigational Product Adherence**

This analysis will be based on the FAS.

IP adherence (%) is defined as the number of capsules taken, divided by the number of capsules planned to be taken, times 100%. The planned number of capsules taken is defined as similar way as planned exposure, with consideration of the Day 84 visit windows (+/- 2 days).

- 1) For participants who complete the treatment period, the planned number of capsules taken is defined as follows:
  - a. 82 if Study Day of Day 84 Visit < 82
  - b. (Date of Day 84 visit – First Dose Date + 1) if Study Day of Day 84 Visit is between 82 and 86 (inclusive)
  - c. 86 if Study Day of Day 84 Visit > 86
- 2) For participants who discontinue the treatment earlier than Day 84 Visit, the planned exposure is (Last Dose Date – First Dose Date + 1).

Number and percentage of participants with IP adherence in categories (<80%, 80-100%, >100%) will be provided. By-participant listing of IP adherence will be provided.

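### SAP 8.2.7 miscounts planned exposure for participants reduced to 0.9 mg before Day 28 who later stop, and its percentage for other early stoppers is an on-treatment ratio

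*SAP*

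**What the plan says.** SAP 8.2.7 defines the measure as follows: "Percent of the planned exposure received is defined as the total drug exposure, divided by planned exposure, times 100". In the numerator, "If a participant skips a dose on any of the days, the dose taken is 0 mg". The denominator depends on which of five rules applies; the fifth only says that the measure does not apply to participants who never received SAGE-718.

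- **Rule 1, completers.** 1.2 mg per day up to the day before the Day 28 visit, then 0.9 mg per day to the Day 84 visit, with limits for visits outside study days 82 to 86.
- **Rule 2, stop before Day 28.** "the planned exposure is (Last Dose Date – First Dose Date + 1) times 1.2 mg for participants randomized to SAGE-718".
- **Rule 3.** "For participants who discontinue the treatment on or after Day 28 but prior to Day 84": 1.2 mg for each day from the first dose to the day before the Day 28 visit, "plus (Last Dose Date of 0.9 mg – First Dose Date of 0.9 mg +1) times 0.9 mg".
- **Rule 4, reduced before Day 28 and kept on 0.9 mg to the end of treatment.** 1.2 mg through the last 1.2 mg dose, then 0.9 mg from the first 0.9 mg dose to a date set by the Day 84 visit (sub-rules a to c).

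SAP 8.2.8 also ends the planned capsule count at the last dose: "For participants who discontinue the treatment earlier than Day 84 Visit, the planned exposure is" the number of days from first to last dose. Protocol 7.4 permits reduction to 0.9 mg. Protocol 7.1 and SAP 5.1 ask participants who stop IP to keep attending the scheduled visits.

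**The concern.** Rules 2 and 3 are written as if the change to 0.9 mg always happens at the Day 28 visit. Nothing in either rule excludes a participant who was reduced earlier. Under rule 3 the 1.2 mg block runs to the Day 28 visit while the 0.9 mg block starts at the actual first 0.9 mg dose, so the two blocks overlap. Under rule 2 the days after a reduction are still planned at 1.2 mg. Rule 4 has no overlap, but its denominator runs to the Day 84 visit, and a participant who stopped IP may still attend that visit. The SAP does not say which rule prevails, so two programmers could report different percentages for the same person.

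The second issue is the label. For early stoppers the denominator ends at their own last dose, so the percentage cannot fall because someone stopped. The primary estimand uses treatment policy for discontinuation, so a reader of a weak Day 84 result will want to know how much of the assigned regimen was delivered. A figure called percent of planned exposure invites that reading and does not supply it.

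**Working it through.** **Inputs.** First dose on Day 1, Day 28 and Day 84 visits on their nominal days, one dose per day, no missed dose up to the stop. Dose levels and switch day come from SAP 5.1. Reduction on Day r means that the first 0.9 mg dose is on Day r.

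**The plan's own figures first.** Rule 1 days = (Day 28 visit − first dose) + 0.9 mg days.

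- Day 84 visit on Day 84: 27 + (84 − 28 + 1) = 27 + 57 = 84.
- Visit before Day 82: 27 + (1 + 82 − 28) = 27 + 55 = 82.
- Visit after Day 86: 27 + (1 + 86 − 28) = 27 + 59 = 86.

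These match the 82 and 86 in SAP 8.2.8. The full assigned regimen is 27 × 1.2 + 57 × 0.9 = 32.4 + 51.3 = 83.7 mg.

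**Reduced on Day 10, stop after Day 40.**

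- Taken: 9 × 1.2 + 31 × 0.9 = 10.8 + 27.9 = 38.7 mg.
- Rule 3 plan: 27 × 1.2 + 31 × 0.9 = 32.4 + 27.9 = 60.3 mg, which is 27 + 31 = 58 doses in 40 calendar days. Percentage: 38.7/60.3 = 64.2%.
- Rule 4 plan, if a Day 84 visit exists and the rule is applied: 9 × 1.2 + 75 × 0.9 = 78.3 mg. Percentage: 38.7/78.3 = 49.4%.
- Share of full regimen: 38.7/83.7 = 46.2%.
- SAP 8.2.8 for the same person: 40 capsules taken of 40 planned = 100%.

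The days counted twice number 28 − r. Here that is 18, and the denominator is too large by 18 × 1.2 = 21.6 mg (60.3 − 38.7). The excess does not depend on the stop day. Other cases:

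| First 0.9 mg dose | Stop after | Taken (mg) | Rule 3 plan (doses) | Rule 3 | Rule 4 plan | Rule 4 | Share of 83.7 mg |
|---|---|---|---|---|---|---|---|
| Day 10 | Day 40 | 38.7 | 60.3 (58) | 64.2% | 78.3 | 49.4% | 46.2% |
| Day 15 | Day 50 | 49.2 | 64.8 (63) | 75.9% | 79.8 | 61.7% | 58.8% |
| Day 8 | Day 70 | 65.1 | 89.1 (90) | 73.1% | 77.7 | 83.8% | 77.8% |

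In the last row the rule 3 plan exceeds the whole 83.7 mg regimen for a participant who stopped two weeks early, and the order of the rule 3 and rule 4 percentages reverses.

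**Reduced on Day 10, stop after Day 20 (rule 2).** Taken: 9 × 1.2 + 11 × 0.9 = 20.7 mg. Plan: 20 × 1.2 = 24.0 mg. Percentage: 20.7/24.0 = 86%. No day is counted twice; the 11 days on 0.9 mg are planned at 1.2 mg.

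**Unreduced stoppers.**

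- Stop after Day 14: SAP 16.8/16.8 = 100%; share of full regimen 16.8/83.7 = 20.1%.
- Stop after Day 56: taken and planned 32.4 + 29 × 0.9 = 58.5 mg, so SAP 100%; share 58.5/83.7 = 69.9%.
- Stop after Day 14 with half the doses missed: 8.4/16.8 = 50%. The ratio responds to missed doses but not to stopping.

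**The case against.** The strongest reply is that ending the denominator at last dose is a deliberate definition. It is spelled out in 8.2.7, used again in 8.2.8, and fits the schedule footnote that adherence is not recorded once IP is stopped. That stands: the truncation is an on-treatment ratio under a misleading name, not an arithmetic error. It does not explain 58 planned doses in 40 days, or rule 4 running to Day 84.

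A second reply is that rule 4 is the specific rule for reduced participants and should prevail, in which case nothing is counted twice. The text does not settle this. Rule 4 describes people who stayed on 0.9 mg until treatment ended, which a later stopper did not do, so rule 3 is the more literal reading. The absence of a stated order is itself the defect.

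Third, a reader might infer that exposure lost to stopping will be invisible. The documents do not support that. SAP 8.2.7 also summarizes total mg and exposure duration, and SAP 8.2.1 reports treatment completion, IP discontinuation with reasons, and reductions before Day 28.

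Fourth, replacing every rule with one full-regimen denominator would score a fully adherent reduced completer at 78.3/83.7 = 93.5%, where rule 4 gives 100%. That is a fair objection to discarding rule 4, and the fix keeps it.

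**Conclusion.** Rules 2 to 4 yield wrong or conflicting percentages for one defined group: participants reduced before Day 28 who later stop IP. With no missed dose, the worked cases give 64% or 49% (rule 3 or rule 4) and 86% (rule 2). For unreduced early stoppers the percentage is internally consistent but is not a share of the planned regimen: 100% against 20% at Day 14 and 70% at Day 56.

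Two broader readings do not hold. Not every early stopper scores 100%; that needs no missed dose and no reduction before Day 28. Not every reduced stopper has days counted twice; that needs a stop on or after Day 28 and the use of rule 3.

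The figures assume nominal visit days. The documents give no expected number of participants who are reduced and then stop, so the effect on the group mean cannot be sized. This is a descriptive Safety Set summary, and no test, alpha level or sample size depends on it. It should be corrected because the reported number would otherwise depend on the programmer's choice of rule.

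**What to change.** In SAP 8.2.7:

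1. For all early stoppers, count each calendar day from first to last dose once, at the dose level assigned on that day: 1.2 mg through the last 1.2 mg dose day (for a reduced participant) or the day before the Day 28 visit, whichever is earlier, and 0.9 mg after that. The two reduced examples then give 38.7/38.7 and 20.7/20.7, both 100%.
2. State that rule 4 a to c applies only to reduced participants who complete treatment, and keep it for them.
3. Label the resulting percentage as on-treatment.
4. Add one descriptive line giving total mg as a percentage of the full assigned regimen through Day 84 (83.7 mg on nominal days). The worked cases would show 46.2% (reduced Day 10, stop Day 40), 20.7/83.7 = 24.7% (reduced Day 10, stop Day 20), and 20.1% and 69.9% for the unreduced stops at Day 14 and Day 56.

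This concerns the denominator only and leaves the protocol's dosing rules untouched. The cost is SAP wording and a few lines of derivation code, with no new data. The added full-regimen figure will look less favourable than the on-treatment one.

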### **8.2.8. Investigational Product Adherence**

This analysis will be based on the FAS.

IP adherence (%) is defined as the number of capsules taken, divided by the number of capsules planned to be taken, times 100%. The planned number of capsules taken is defined as similar way as planned exposure, with consideration of the Day 84 visit windows (+/- 2 days).

- 1) For participants who complete the treatment period, the planned number of capsules taken is defined as follows:
  - a. 82 if Study Day of Day 84 Visit < 82
  - b. (Date of Day 84 visit – First Dose Date + 1) if Study Day of Day 84 Visit is between 82 and 86 (inclusive)
  - c. 86 if Study Day of Day 84 Visit > 86
- 2) For participants who discontinue the treatment earlier than Day 84 Visit, the planned exposure is (Last Dose Date – First Dose Date + 1).

Number and percentage of participants with IP adherence in categories (<80%, 80-100%, >100%) will be provided. By-participant listing of IP adherence will be provided.

## **8.3. Efficacy Analysis**

### **8.3.1. Definition of Efficacy Variable(s)**

#### **8.3.1.1. Primary Efficacy Assessment**

The Symbol Digit Modalities Test is widely used to monitor changes in cognitive function over time and for early detection of cognitive dysfunction. The task requires participants to

use a reference key to pair specific numbers with geometric figures. The number of correct pairings (out of 110 possible) achieved within 90 seconds is summed to generate a total score.

The SDMT will be assessed on Screening Period (Day -28 to -2 and Day -1), Day 14, Day 28, Day 84, and Day 112.

### **8.3.1.2. Key Secondary Efficacy Assessments**

Key secondary outcomes are Change from Baseline to Day 84 in 1) UHDRS-Independence Scale; 2) Trail Making B (TMT-B) in a subgroup of participants who were able to complete the test within 240 seconds (yes/no) at Baseline; 3) One Touch Stockings of Cambridge (OTS) ; 4) Paced Tapping Test (PTAP); 5) Huntington’s Disease Everyday Functioning (Hi-DEF) – at home subdomain score; 6) Clinical Global Impression – Severity (CGI-S) – cognitive status subdomain score.

#### **8.3.1.2.1.1. UHDRS – Independence Scale**

The Independence Scale (Part V) is a part of the Unified Huntington’s Disease Rating Scale (UHDRS) described in detail in Section 8.3.1.3.7. It is intended to assess the ability of the participant to function independently in activities of daily living across the full spectrum of the disease. A single independence rating is provided on a scale ranging from 10 to 100, with higher scores reflecting better functioning.

The UHDRS – Independence Scale will be assessed on Screening Period (Day -28 to -2 and Day -1), Day 28, Day 84, and Day 112.

#### **8.3.1.2.1.2. Trail Making B (TMT-B)**

The Trail Making test is a timed graphomotor test of visual attention and task switching, administered in two parts. Only part B will be used for the key secondary analysis. Part B -requires the examinee to connect a series of alternating numbers and letters in order from lowest to highest, as in 1-A-2-B-3-C..., in the shortest time possible. The primary measure for analysis is time to completion. Standard administration of the TMT-B uses a 300 second time limit, at which point the test is stopped and scored using the maximum allowable time if not yet completed. The developers of the HD-CAB have adopted a briefer limit of 240 seconds to reduce overall duration of testing, fatigue, and frustration. However, a floor effect is an acknowledged concern that reduces the TMT-B’s ability to distinguish impairment levels among individuals unable to complete within the standard time limit (Abreu et al., 2021). This shorter time limit used by the HD-CAB may further compromise the test’s sensitivity to measure drug effects when scored using the maximum allowable time. For this reason, an inclusion criterion was added to the study protocol in amendment 4 version 5. Accordingly, scores of 240 are considered unevaluable for purposes of this study and the key secondary

analysis in this study will be done within a subgroup of participants who were able to complete the test within the allowable time.

The TMT-B test will be assessed on Screening Period (Day -28 to -2 and Day -1), Day 14, Day 28, Day 84, and Day 112.

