#### **11.2.3.2. Trail Making**

The Trail Making test is a speeded graphomotor test of visual attention and task switching,

[REDACTED] Part B includes an additional set-switching component, requiring the examinee to connect a series of alternating numbers and letters in order from lowest to highest, as in 1-A-2-B-3-C..., in the shortest time possible. The primary measure for analysis is time to completion.

Standard administration of Part B uses a 300 second time limit, at which point the test is stopped and scored using the maximum allowable time if not yet completed. The developers of the HD-CAB have adopted a briefer limit of 240 seconds to reduce overall duration of testing, fatigue, and frustration (Stout 2014b). However, a floor effect is an acknowledged concern that reduces Part B's ability to distinguish impairment levels among individuals unable to complete within the standard time limit (Smith Watts 2019; Abreu 2021). This shorter time limit used by the HD-CAB may further compromise the test's sensitivity to measure drug effects when scored using the maximum allowable time. For this reason, inclusion criterion #15 was added to the study protocol (in effect since Amendment 4, Version 5). Accordingly, scores of 240 at baseline are considered unevaluable for purposes of this study and the key secondary endpoint will be tested within a subgroup of participants who were able to complete the test within the allowable time.

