## 2. INTRODUCTION

This statistical analysis plan (SAP) is for the final analysis for study protocol SAGE-718-CIH-201 and is based on the following approved study documents:

- Study Protocol v6.0, Amendment 5 (19 August 2024)
- electronic Case Report Form (eCRF), Version 12.0 (09 July 2024)

This SAP addresses the objectives of the study and describes the planned statistical analyses and data presentations. All analyses and data presentations will be generated using SAS® Version 9.4 or higher Software (SAS Institute, Cary, North Carolina, USA). This SAP will be finalized and approved before the clinical database lock and treatment unblinding. Any changes made to the SAP after the clinical database lock will be documented and discussed in the clinical study report for this study.

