#### 4.2.1. Key Secondary Endpoint

1. CFB to Day 84 on the Unified Huntington's Disease Rating Scale (UHDRS) - Independence Scale.
2. CFB to Day 84 on the Trail Making Part B (TMT-B) in the subgroup of participants who completed Trail Making Test Part B (TMT-B) at Baseline within the allowable time limit (240 sec)
3. CFB to Day 84 on the One Touch Stockings of Cambridge (OTS-Mean Latency until Correct response [OTS-MLC])
4. CFB to Day 84 on the Paced Tapping Test (PTAP)
5. CFB to Day 84 in Huntington's Disease Everyday Functioning (Hi-DEF) – at home subdomain score
6. CFB to Day 84 in Clinical Global Impression – Severity (CGI-S) – cognitive status subdomain score

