## **6. MODIFICATIONS**

### **6.1. Modifications from the Approved Clinical Study Protocol**

Protocol Amendment 5 - change the primary endpoint from CFB Day 84 on HD-CAB composite score to CFB Day 84 SDMT, upgraded some secondary endpoints to key secondary endpoints, [REDACTED] and clarify the plan to conduct database lock in two parts. The SAP was adjusted to incorporate the changes described above.

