- 5) The population summary level deals with the difference between SAGE-718 and placebo treatments in mean change from baseline to Day 84 in Symbol Digit Modalities Test (SDMT) The primary efficacy endpoint is the change from baseline to Day 84 on the SDMT score. This primary endpoint will be analyzed using a mixed-effects model for repeated measures (MMRM). The model will include baseline SDMT score as a continuous explanatory variable, treatment, assessment time point, and time point-by-treatment as categorical explanatory variables. The Kenward-Roger correction to degrees of freedom will be applied. All explanatory variables will be treated as fixed effects in the model. All post-baseline time points will be included in the model. An unstructured (UN) covariance matrix with the default Newton-Raphson optimization algorithm as implemented in the SAS procedure PROC MIXED will be used to estimate the within-subject correlation. If this model fails to converge, the Fisher Scoring algorithm (via the SCORING option of the PROC MIXED statement), the no-diagonal factor analytic structure (via the TYPE=FA0( $T$ ) option of the REPEATED statement, where  $T$  is the total number of time points), Toeplitz, Autoregressive (1) [AR (1)], Compound symmetry (CS) covariance structure will be used, following this sequence until convergence is achieved. If the model still does not converge with CS structure, the Glimmix procedure with option of parametrizing UN to Cholesky root matrix will be used and in the case it also does not converge no results will be reported. When the covariance structure is not UN, the sandwich estimator for the variance-covariance matrix will be derived, using the EMPIRICAL option in the PROC MIXED statement in SAS. The primary comparison will be between SAGE-718 and placebo at the Day 84. Least squares means and 95% confidence interval will be summarized, and the p-value from the hypothesis test of no difference between the treatment groups will be also presented.

A plot showing the LS means of SDMT score  $\pm$  SE bar over time within each treatment group will be provided.

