### 8.3.3.2. Sensitivity Analysis of Primary Endpoint

Sensitivity analysis is planned if >5% of participants in any treatment group have missing data in the primary endpoint or the values could not be used due to the use of prohibited medications.

If any of the sensitivity analyses yields a result that is in a different direction from the result of the primary analysis, the nature of the discrepancy will be examined to clearly explain the discrepancy based on statistical principles and the discrepancy will be discussed in the CSR.

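### The SAP's rule that Trail Making B scores of 240 are unevaluable omits the protocol's limit to baseline; read literally, it deletes post-baseline time-outs

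*SAP*

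**What the plan says.** Protocol 11.2.3.2 (Trail Making) explains that the cognitive battery stops Part B at 240 seconds, that a floor effect is a concern, and that inclusion criterion 15 was added for this reason. It then says: "Accordingly, scores of 240 at baseline are considered unevaluable for purposes of this study".

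SAP 8.3.1.2.1.2 repeats nearly the whole paragraph, but the sentence reads: "Accordingly, scores of 240 are considered unevaluable for purposes of this study". The clause that follows, on the subgroup to be analysed, names no time point either.

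Elsewhere the SAP ties the subgroup to baseline. Sections 4.2.1, 8.3.1.2, 8.3.4 and 8.3.5 define the key secondary endpoint in participants who completed the test within 240 seconds at baseline, and 8.3.3.4 uses the same baseline split as a subgroup factor.

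On scoring, SAP 8.3.1.2.1.2 says that in standard administration, with a 300-second limit, an unfinished test is "scored using the maximum allowable time if not yet completed". This is background to the concern about the floor effect.

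SAP 8.3.4 analyses the key secondaries in the same way as the primary endpoint, that is, by the MMRM of 8.3.3.1, where "All post-baseline time points will be included in the model". SAP 8.3.3.2 reads: "Sensitivity analysis is planned if >5% of participants in any treatment group have missing data in the primary endpoint".

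SAP Section 2 bases the SAP on protocol version 6.0 (Amendment 5). Section 6.1 lists what that amendment changed and adds: "The SAP was adjusted to incorporate the changes described above". Its visible text does not mention the scoring of Trail Making B.

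**The concern.** The passages that mention baseline settle who is analysed. They do not settle what happens when someone in that subgroup fails to finish within 240 seconds at a later visit. In the visible SAP, the only sentence that gives a status to a score of 240 is the one in 8.3.1.2.1.2, and it has no time limit. A programmer who set every 240 to missing would be following the text.

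For this test a longer time is worse, so a 240 is the worst possible result. Setting it to missing makes missingness depend on the unobserved value, whereas the MMRM assumes missing at random. If the drug works, placebo participants time out more often, so deletion removes more bad outcomes from placebo and shrinks the difference. If the drug harms, the harm is understated in the same way. The visible missing-data sensitivity analyses cover the primary endpoint only.

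Trail Making B is second of the six key secondaries, so third in the fixed sequence after SDMT and the Independence Scale. It gates four endpoints: OTS, PTAP, Hi-DEF at home and CGI-S cognitive status.

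**Working it through.** **1. The text.**

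| Question | Protocol 11.2.3.2 | SAP 8.3.1.2.1.2 | Other visible SAP text |
|---|---|---|---|
| Who is in the analysis? | Baseline completers | Completers, no time point | Baseline completers |
| Which 240s are unevaluable? | Those at baseline | All, no time point | Silent |
| How is a post-baseline 240 scored? | No explicit rule | Unevaluable if read literally | Silent |

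**2. Size: inputs.** The plan has no Trail Making B figure to reproduce, so every Trail Making B input below is an assumption. The 71 per arm is the SDMT target from SAP 5.2. That sizing checks out for SDMT: with a difference of 4, SD 7.3 and two-sided alpha 0.05, the noncentrality is 4 / (7.3 × √(2/71)) and t-test power is 90.0%. The Trail Making B subgroup may be smaller.

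**3. Model.**
- Baseline B is normal with SD 50, truncated to 30–240 s, so that only completers enter.
- The score at visit j is Y = min(240, B + e + f × δ × treatment), where δ is the true Day 84 effect in seconds (negative is benefit) and f = 0.4, 0.7 and 1.0 at Days 14, 28 and 84, the three visits in the SAP Appendix B imputation code.
- The errors e have the SD of change and the between-visit correlation shown below (compound symmetry).
- The analysis is an MMRM of change on treatment, visit, treatment-by-visit and baseline, with unstructured covariance. The same data are analysed twice: 240s kept at 240, and post-baseline 240s set to missing.
- Estimates come from 8 runs of 50,000 per arm (maximum likelihood, Monte Carlo SE 0.03–0.13 s). Power comes from 10,000 trials of 71 per arm (REML, t test with 138 df, Monte Carlo SE 0.5 points).

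**4. Results at Day 84** (times in seconds).

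| | Baseline mean | SD of change | Correlation | True effect | Kept | Dropped | Extra loss | Loss / true effect | Power kept / dropped |
|---|---|---|---|---|---|---|---|---|---|
| A | 140 | 35 | 0.5 | -12 | -11.4 | -11.0 | 0.4 | 0.4/12 = 3% | 52% / 50% |
| B | 155 | 40 | 0.5 | -15 | -14.0 | -13.2 | 0.8 | 0.8/15 = 5% | 58% / 54% |
| C | 170 | 45 | 0.3 | -15 | -13.6 | -12.3 | 1.3 | 1.3/15 = 9% | 49% / 40% |
| D | 170 | 45 | 0.7 | -15 | -13.5 | -12.6 | 0.9 | 0.9/15 = 6% | 49% / 44% |

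Time-outs at Day 84 were 3.7–10.3% on placebo and 2.1–6.3% on drug. The power loss is about 2 to 8 points (scenario C shows 9 only through rounding).

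With no true effect, both rules gave estimates within 0.12 s of zero. Rejection rates were 4.8–5.2% with 240s kept and 4.8–5.1% with them dropped (Monte Carlo SE 0.2 points). A harm of the same size was attenuated by 3–10%.

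**5. Stability.** A separate fit of the four scenarios gave, kept / dropped, -11.5/-11.2, -14.2/-13.4, -13.5/-12.3 and -13.9/-13.0 s. Absolute values move by up to about 0.4 s. The extra losses, 0.3, 0.8, 1.2 and 0.9 s, agree closely with the table.

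A simpler single-visit ANCOVA (baseline mean 120–180 s, SD of change 30–40 s, true benefit 15 s) gave 13.7–14.9 s kept and 12.5–14.7 s dropped. For a true harm of 15 s it gave 12.9–14.6 s kept and 11.8–14.4 s dropped. The direction is the same.

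**The case against.** The strongest reply is that context already supplies the missing words. The sentence draws a conclusion from the entry criterion and runs straight into the subgroup restriction. That restriction also lacks a time point there, yet the rest of the SAP plainly means baseline. The SAP rests on the current protocol and announces no change. Calling a score unevaluable is also not an explicit instruction to set it to missing. Protocol 13.2 says all non-missing data will be used, and the primary model takes in every post-baseline visit. Redacted parts (most of SAP 8.3.1.3 with Table 2, Table 3 in 8.3.2, and most of 8.3.6) may hold a scoring rule. Finally, both documents warn that scoring at the maximum time may reduce sensitivity, so the 240 s cap is not the only defensible choice.

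Much of this stands. A slip is the likely explanation, the redactions limit what can be said about the full SAP, and the scoring rule is the sponsor's to state. But using all available data, or all visits, does not rescue a score that the SAP itself calls unevaluable. Reading the subgroup as baseline completers still leaves their later time-outs without a rule. The warning about maximum-time scoring does not favour deletion either: in the scenarios above, deletion attenuates more than the cap.

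**Conclusion.** The point holds and is minor. It is certain that the SAP omits the protocol's limit to baseline and that its visible text gives no other rule for post-baseline time-outs.

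The consequence is conditional. It needs a programmer to follow the sentence literally and baseline completers to time out later. It reaches formal testing only if SDMT and the Independence Scale are both significant. The result would then be modest attenuation toward zero and some loss of power, in a test whose success opens four more. The sizes in the table illustrate the mechanism under assumed inputs and three post-baseline visits (the SAP also lists Day 112). They are not a forecast for this trial, and the first decimal of the absolute estimates should not be relied on.

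**What to change.** In SAP 8.3.1.2.1.2, restore the protocol's wording: "Accordingly, scores of 240 at baseline are considered unevaluable for purposes of this study". Then add one sentence, before unblinding: in the subgroup that completed Part B within 240 s at baseline, a post-baseline time-out is analysed as 240 s. If the sponsor intends another rule, it should be recorded and justified in SAP 6.1.

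The cost is two words and one sentence, with no new data or analysis. The cap has a small price of its own: in the table a true -12 s appears as -11.4 s, and a true -15 s as -13.5 to -14.0 s. Deletion costs more, giving -11.0 s and -12.3 to -13.2 s. Settling the rule after unblinding would turn it into a data-dependent choice on an endpoint under multiplicity control.
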